4.2 Statistical and Analytical Methods

4.2.1 Analysis Populations and Analysis Groups

Population of Patients Enrolled [EP]

The population of patients enrolled comprises all patients who voluntarily sign and date an informed consent prior to inclusion into the study and data were captured in the eCRF.

Target Population [TP]

Patients will be included if the following applies:

- Age at least 18 years
- Confirmed CHC with genotype 1 and/or 4 only, receiving combination therapy with the interferon-free ABBVIE REGIMEN \pm RBV. The prescribed ABBVIE REGIMEN needs to be known.
- Have voluntarily signed and dated an informed consent prior to inclusion into the study
- Must not be participating or intending to participate in a concurrent interventional therapeutic trial

Core Population [CP]

The core population is defined as all patients of the target population (TP) (definition see above), who are adequately treated according to the standard of care and within local label recommendations for their specific disease characteristics (cirrhotic status, genotype). The following patients will be excluded from the CP:

- Patients with unknown fibrosis status
- Cirrhotic patients with genotype 1a not receiving ribavirin
- Patients with genotype 1 for whom 2DAA instead of 3DAA is prescribed
- Patients with genotype 4 not receiving RBV

Non-Core Population [NCP]

Patients in the TP who are not in the CP.

Core Population with Sufficient Follow-up [CPSFU {12, 24}]

In addition, the core population with sufficient follow-up data regarding SVR12 or SVR24, respectively, is defined as all CP patients,

- who have evaluable HCV RNA data ≥ 70 days or >126 days, respectively, after the last actual dose of the ABBVIE REGIMEN
- or a HCV RNA value ≥ 50 IU/mL at the last measurement
- or had HCV RNA <50 IU/mL at the last measurement, but no HCV RNA measurement ≥ 70 days or >126 days, respectively, after the last actual dose of the ABBVIE REGIMEN due to reasons related to safety (e.g. dropped out due to adverse event) or virologic failure (e.g. virologic failure such as relapse is reported in the electronic case report form (eCRF) but date and value of the corresponding HCV RNA test is missing).

This means only patients who had virological response at their last on-treatment or post-treatment measurement, but had no HCV RNA measurements ≥ 70 days or >126 days, respectively, post-treatment for reasons not related to safety or effectiveness (e.g. lost-to-follow-up or patient not willing to perform an additional HCV RNA test ≥ 70 days or >126 days, respectively, post-treatment) will be excluded from this analysis.

Safety population [SP]

The safety population is defined as all enrolled patients who received at least one dose of the ABBVIE REGIMEN. The prescribed ABBVIE REGIMEN needs to be known.

EP and TP analysis groups

The EP/TP analysis groups are defined according to the patient's fibrosis status and genotype/subtype and standard summaries are structured as follows:

- Total (regardless of cirrhosis status)
 - (1) Total (regardless of genotype)
 - (2) G1 (Total)
 - (3) G1a (including mixed G1 subtypes and patients with G1 unknown subtype)
 - (4) G1b
 - (5) G4 (non-G1)
 - (6) Other/unknown genotype (*only for EP*)
- Patients with cirrhosis
 - (7) Total (regardless of genotype)
 - (8) G1 (Total)
 - (9) G1a (including mixed G1 subtypes and patients with unknown G1 subtype)
 - (10) G1b
 - (11) G4 (non-G1)
 - (12) Other/unknown genotype (*only for EP*)
- Patients without cirrhosis
 - (13) Total (regardless of genotype)
 - (14) G1 (Total)
 - (15) G1a (including mixed G1 subtypes and patients with unknown G1 subtype)
 - (16) G1b
 - (17) G4 (non-G1)
 - (18) Other/unknown genotype (*only for EP*)
- Patients with unknown fibrosis status
 - (19) Total (regardless of genotype)
 - (20) G1 (Total)
 - (21) G1a (including mixed subtypes and patients with unknown subtype)
 - (22) G1b
 - (23) G4 (non-G1)
 - (24) Other/unknown genotype (*only for EP*)

(HCV genotypes will be combined as follows: G1 [total], G1a*, G1b, G4 [non-G1]. * includes mixed or other G1 subtypes and patients with unknown G1 subtypes.

Most recent stage of liver fibrosis will be categorized as follows: No cirrhosis/Transition to cirrhosis, Cirrhosis. Only one method should be selected by the physicians to report stage of fibrosis. Nevertheless, if there are multiple answers the following priority will be used:

1. Biopsy,
2. Non-invasive,
3. Clinical/best guess.

For biopsy as assessment method the respective categories are defined as follows:

- “No cirrhosis” is defined by “No fibrosis”, “Mild/minimal fibrosis”, “Moderate fibrosis”
- “Transition to cirrhosis” is defined by “Advanced Fibrosis”
- “Cirrhosis” is defined by “Cirrhosis”.)

CP analysis groups and related treatment regimens

The CP analysis groups are defined according to the patient's fibrosis status and genotype/subtype. The standard summaries by CP analysis groups in the CP and CPSFU population are structured follows (is not specified otherwise):

- Total (regardless of cirrhosis status)
 - (1) Total (regardless of genotype)
 - (2) G1 (Total)
 - (3) G1a (including mixed subtypes and patients with unknown subtype)
 - (4) G1b
 - (5) G4 (non-G1)
- Patients with cirrhosis
 - (6) Total (regardless of genotype)
 - (7) G1 (Total)
 - (8) G1a (including mixed subtypes and patients with unknown subtype)
 - (9) G1b
 - (10) G4 (non-G1)
- Patients without cirrhosis
 - (11) Total (regardless of genotype)
 - (12) G1 (Total)
 - (13) G1a (including mixed subtypes and patients with unknown subtype)
 - (14) G1b
 - (15) G4 (non-G1)

SP analysis groups

The SP analysis groups are defined according to the treatment regimen and patient's fibrosis status. The standard summaries by SP groups in the safety population are as follows (if not specified otherwise):

- Total (regardless of cirrhosis status)
 - (1) Total
 - (2) 2DAA w/o RBV
 - (3) 2DAA + RBV
 - (4) 3DAA w/o RBV
 - (5) 3DAA + RBV
- Patients with cirrhosis
 - (6) Total
 - (7) 2DAA w/o RBV
 - (8) 2DAA + RBV
 - (9) 3DAA w/o RBV
 - (10) 3DAA + RBV
- Patients without cirrhosis
 - (11) Total
 - (12) 2DAA w/o RBV
 - (13) 2DAA + RBV
 - (14) 3DAA w/o RBV
 - (15) 3DAA + RBV
- Patients with unknown fibrosis status
 - (16) Total
 - (17) 2DAA w/o RBV
 - (18) 2DAA + RBV
 - (19) 3DAA w/o RBV
 - (20) 3DAA + RBV

(2DAA - paritaprevir/r-ombitasvir, 3 DAA - paritaprevir/r-ombitasvir + dasabuvir, RBV – ribavirin taken, w/o RBV – no ribavirin taken)

NCP analysis groups

The summary tables for the NCP will only show the data pooled for all patients in the NCP without any subgrouping by genotype and/or fibrosis status.

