#### **Data Analysis:**

The core population (CP) is defined as all patients of the target population (TP) (definition see above), who have started the treatment combination recommended in the current local label for their disease characteristics. Patients not receiving the treatment recommended in the local label will be summarized in the non-core population (NCP). In addition, the core population with sufficient follow-up data (CPSFU) is defined as all CP patients, who have (i) evaluable HCV RNA data  $\geq$  70 days after the last actual dose of the ABBVIE REGIMEN or (ii) a HCV RNA value  $\geq$  50 IU/mL at the last measurement or (iii) had HCV RNA  $<$  50 IU/mL at the last measurement, but no HCV RNA measurement  $\geq$  70 days after the last actual dose of the ABBVIE REGIMEN

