## 9.7 Data Analysis

### 9.7.1 Analysis Population, Time Windows and Handling of Missing Data

The target population (TP) is defined as all patients who fulfill the criteria specified in Section 9.2.1. The core population (CP) is defined as all patients of the TP, who have started the treatment combination recommended in the current local label for their disease characteristics. Patients not receiving the treatment recommended in the local label will be summarized in the non-core population (NCP). In addition, the core population with sufficient follow-up data (CPSFU) is defined as all CP patients, who fulfil one of the following criteria:

- (1) evaluable HCV RNA data  $\geq 70$  days after the last actual dose of the ABBVIE REGIMEN (i.e. data within the SVR12 time window)
- (2) a HCV RNA value  $\geq 50$  IU/mL at the last measurement post-baseline (i.e. no virological response achieved at the last measurement on-treatment or post-treatment)
- (3) HCV RNA  $< 50$  IU/mL at the last measurement post-baseline, but no HCV RNA measurement  $\geq 70$  days after the last actual dose of the ABBVIE REGIMEN due to reasons related to safety (e.g. dropped out due to AE) or incomplete efficacy information (e.g. virologic failure such as relapse is reported in the eCRF but date and value of the corresponding HCV RNA test is missing). This means only patients who had virological response at their last on-treatment or post-treatment measurement, but had no HCV RNA measurements  $\geq 70$  days post-treatment for reasons not related to safety or effectiveness (e.g. lost-to-follow-up or patient not willing to perform an additional HCV RNA test  $\geq 70$  days post-treatment) will be excluded from this analysis.

The Safety Population (SP) is defined as all patients who received at least one dose of the ABBVIE REGIMEN.

In accordance with the non-interventional nature of the study all HCV RNA measurements will be performed at the sole discretion of the physician and all HCV RNA measurements have to be entered into the eCRF. All recorded HCV RNA values will be assigned to appropriate time points (baseline, on-treatment visits, EoT visit, post-

---

Confidential Information

No use or disclose outside AbbVie is permitted without prior written authorization from AbbVie

---

treatment visits). The time windows for the assignments will be specified in the statistical analysis plan (SAP).

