4.2.2 Definition of Baseline and Visit Time Windows

This observational study covers three documentation periods, see Figure 1. An overview of data to be collected throughout the study is summarized in Table 2.

Table 2 - Data Documentation Schedule

Assessment/ Procedure (only available data to be collected; no diagnostic or monitoring procedures to be applied to the patients apart from those of routine clinical practice)	Baseline	Treatment Period			Post-treatment (PT) Period		
		On-treatment visits	Mid treatment visit for pts receiving 24 weeks of therapy	EoT ^b	Early PT visit	SVR 12 visit	SVR 24 visit
Informed Consent	X ^a						
Demographic information	X						
IL28B	X						
Relevant CHC disease characteristics	X						
Liver fibrosis stage	X						
CHC treatment history	X						
HCV genotype and subtype	X						
HCV RNA samples	X	X	X	X	X	X	X
Clinical chemistry and hematology	X	X	X	X	X	X	X
ABBVIE REGIMEN initiation documentation	X						
ABBVIE REGIMEN adherence		X	X	X			
Concomitant medication	X	X	X	X			
Relevant medical history, co-morbidities	X						
sAE, AE and pregnancy reporting	X	X	X	X	X ^c	X ^d	X ^d
For patients receiving RBV: Evidence, in accordance with local label, that female patient or female partner of male patient is not pregnant	X						
Viral resistance sample	X			X		X	X
Patient questionnaires – PAM-13, BMQ 18-item	X			X			
PSP evaluation		X	X	X	X	X	

Abbreviations: EoT = End of Treatment (at Week 12 or 24 or at premature discontinuation),
PT = Post-Treatment

a Written informed consent must be obtained before any data documentation in the eCRF

b Patients who prematurely discontinue should return to the site to document EoT data

c Tolerability documentation until PT week 4

d Pregnancy reporting for patients treated with DAA plus RBV

In accordance with the non-interventional nature of the study all HCV RNA measurements will be performed at the sole discretion of the physician and all HCV RNA measurements have to be entered into the eCRF. All recorded HCV RNA values will be assigned to appropriate time points (baseline, on-treatment visits, EoT visit, post-treatment visits) as follows:

Table 3 - Analysis Time Windows for HCV RNA

Phase	Time point	Time Window
Pre-Treatment	Baseline	Last value prior to start of study treatment (i.e. \leq study day 1)
On-treatment		Study day during treatment period ^{^#} (Study day 1 = first treatment day)
Treatment Week	4 (RVR*)	15 - 42 [^]

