4.2.3 Handling of missing data

No data will be imputed for any effectiveness or safety analyses except for the analyses of the HCV RNA endpoints and certain PRO endpoints. The discussion of missing data imputation for the PRO endpoints is included in section 4.2.7.2.3.

HCV RNA values will be selected for an RVR, EOTR and SVR analysis based on visit windows as defined in Table 3. When there is no HCV RNA value in a visit window based on defined visit windows, the closest values before and after the window, regardless of the value chosen for the subsequent and preceding window, will be used for the flanking imputation described below. For analysis of RVR, EOT and SVR, if a subject has a missing HCV RNA value at a post-Day 1 visit but with undetectable or unquantifiable (\leq 50 IU/mL) HCV RNA levels at both the preceding value and succeeding value, the HCV RNA level will be considered undetectable or unquantifiable, respectively, at this visit for this subject. In addition, if a subject has an unquantifiable HCV RNA level at the preceding value and an undetectable HCV RNA level at the succeeding value, or vice versa, the HCV RNA level will be imputed as unquantifiable at this visit for this subject.

For analyses of RVR, subjects still missing a value for the visit after flanking imputation will be imputed as a failure. For EoTR and SVR analysis, if there is no value in the appropriate window after flanking imputation but there is an HCV RNA value after the window, then it will be imputed into the EoTR or SVR window respectively. Subsequent to this flanking imputation, if a subject is missing a value for the visit window associated with the analysis, the subject will be imputed as a visit failure (i.e., not undetectable or unquantifiable).

If a subject starts another treatment for HCV, then all HCV RNA values for this subject measured on or after the start date of the new HCV treatment will be excluded from analyses. The subject will be considered a failure for summaries of viral response at all time points after the start of the new HCV treatment.

Due to the non-interventional nature of this study several different methods for determination of the HCV RNA value can be applied. For the purpose of the statistical analysis, a HCV RNA measurement is considered ≤ 50 IU/mL,

- if a PCR test was used

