4.2.7 Analyses of the Objectives

4.2.7.1 Primary Effectiveness Variable

The primary objective of this study is to estimate the SVR12 rates in HCV patients treated according to the ABBVIE Regimen.

Therefore the simple percentage of patients achieving SVR12 (for definition see section 4.1.1) will be calculated and a two-sided 95% confidence interval (CI) of the percentage will be computed based on the Wilson's Score method.

The primary effectiveness analysis on clinical outcomes will be performed on all patients in the CP stratified by genotype and cirrhosis status and overall.

In the framework of sensitivity analyses the primary analyses will be repeated for the CPSFU. Furthermore, the SVR12 rates will be also determined for all patients of the NCP.

An overview of Tables is given in Table 8.

The layouts of the tables mentioned above are provided in Part II of the SAP (Table Shells).

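### SAP 4.2.1 omits the post-baseline restriction from the sufficient-follow-up criteria, so a patient tested only at baseline can enter CPSFU as a failure

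*SAP*

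**What the plan says.** CPSFU is meant to hold core population (CP) patients whose virological outcome is adequately documented. The documents define it three times, and not in the same way.

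- **Protocol 9.7.1**, criterion 2, admits a value of at least 50 "IU/mL at the last measurement post-baseline (i.e. no virological response achieved at the last measurement on-treatment or post-treatment". Criterion 3 (a last value below 50 IU/mL, with the late test missing for safety or efficacy-reporting reasons) is also limited to post-baseline values.
- **Protocol abstract, Data Analysis**, states criterion (ii) without that limit: "IU/mL at the last measurement or (iii) had HCV RNA".
- **SAP 4.2.1** reads "or a HCV RNA value ≥ 50 IU/mL at the last measurement". Neither its second nor its third criterion mentions post-baseline values. The same list serves CPSFU12 and CPSFU24.

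Both SAP 4.2.1 and protocol 9.7.1 end with a summary of who is left out. It begins "This means only patients who had virological response at their last on-treatment or post-treatment measurement, but had no HCV RNA measurements" and is limited to patients whose late test is missing for reasons unrelated to safety or effectiveness.

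CPSFU has three uses. SAP 4.2.7.1 says "In the framework of sensitivity analyses the primary analyses will be repeated for the CPSFU". SAP 4.2.7.2.1 names the respective CPSFU as the population for the SVR24 rate. SAP 4.2.9 reports the interim non-response rates in CPSFU12.

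**The concern.** HCV RNA testing is at the physician's discretion (SAP 4.2.2), so a CP patient may have a baseline value and nothing afterwards. For that patient the last measurement is the pre-treatment viral load. The SAP criterion then treats a value taken before the first dose as evidence of failure.

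The result runs against the purpose of the population. A patient with a documented response who is then lost is removed for insufficient follow-up. A patient with no follow-up test at all is kept and counted as a failure.

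Protocol 9.9 warns that missing follow-up HCV RNA can lead to underestimation of the SVR rate. CPSFU is the planned SVR12 rate that sets most of that missingness aside, and the literal SAP wording puts part of it back.

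**Working it through.** **1. The plan's own figures.** Exact Clopper-Pearson limits with x = n × p reproduce SAP Table 1:

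- 417 at 90%: 86.71 to 92.71, width 6.00.
- 238 at 95%: 91.41 to 97.40, width 5.99.
- 334 at 95%: 92.08 to 97.08, width 5.00 from the rounded limits (4.99 unrounded).

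Enrolment: 417/0.95 = 438.9, so 439 against the stated 440. Conversely 440 × 0.95 = 418. The sample size does not depend on the CPSFU wording; these figures only set the scale.

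**2. The criteria applied to one patient.** Take a CP patient whose only HCV RNA value is a baseline value of at least 50 IU/mL.

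| Criterion | Protocol 9.7.1 list | SAP 4.2.1 list |
|---|---|---|
| 1. Evaluable value at or beyond 70 days (CPSFU12) or beyond 126 days (CPSFU24) | not met | not met |
| 2. Last value 50 IU/mL or more | not met: no post-baseline value | met through the baseline value |
| 3. Last value below 50 IU/mL, late test missing for safety or failure | not met | not met |
| Result | outside CPSFU | inside CPSFU |

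The protocol column uses the 70-day condition only, since protocol 9.7.1 has no separate CPSFU24. Baseline does count as an HCV RNA measurement: SAP Table 3 assigns recorded values to it and defines it as "Last value prior to start of study treatment". The closing sentence does not remove this patient, because it excludes only those with a response on or after treatment.

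**3. How the patient is counted.** Under SAP 4.2.3, flanking imputation needs favourable values on both sides of the window, and the later-value rule needs a value after it. A baseline-only patient has neither. The remaining rule applies: "if a subject is missing a value for the visit window associated with the analysis, the subject will be imputed as a visit failure".

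**4. Size.** Let m be the CPSFU patients with real follow-up, x the responders among them, and k the baseline-only patients. The rate is x/(m + k), and the fall from x/m is (x/m) × k/(m + k). The documents give no value for k, so every k is an assumption. With m = 418, and x = 397 (about 95%) or 376 (about 90%):

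| k | Rate, x = 397 | Fall (points) | Rate, x = 376 | Fall (points) |
|---|---|---|---|---|
| 0 | 397/418 = 94.98% | – | 376/418 = 89.95% | – |
| 1 | 397/419 = 94.75% | 0.23 | 376/419 = 89.74% | 0.21 |
| 4 | 397/422 = 94.08% | 0.90 | 376/422 = 89.10% | 0.85 |
| 9 | 397/427 = 92.97% | 2.00 | 376/427 = 88.06% | 1.90 |
| 18 | 397/436 = 91.06% | 3.92 | 376/436 = 86.24% | 3.71 |

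Each such patient costs about 0.2 points. The last row is an extreme: 418 + 18 = 436 of 440 enrolled, which leaves 4 patients to cover every non-core exclusion and every responder lost to follow-up.

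**The case against.** The best defence is that the intended meaning can be recovered. The population is named for sufficient follow-up, the closing sentence speaks of on-treatment and post-treatment measurements, and protocol 9.7.1 explains criterion 2 in those terms. A programmer with both documents open might well restrict to post-baseline values. That is fair as to intent. But the SAP criterion does not say it, and the documents do not agree with each other, so the outcome depends on which text the programmer follows.

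Four stronger readings are tempting, and the documents do not support them.

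- *The primary result is biased by this wording.* It is not. The primary SVR12 analysis uses the whole CP, where a missing value is already a failure, so the rate is the same under either wording.
- *The SAP silently departed from a clear protocol.* Only in part. The SAP does flag other departures (the upper limit of the SVR12 window, the interim timing) and not this one. But the protocol abstract already lacks the restriction, and the closing sentence in protocol 9.7.1 conflicts with that section's own list for untested patients.
- *CPSFU is the only planned output that separates virological failure from missing data.* The non-response table in SAP 4.2.7.2.1 has a missing-data category, and SAP 4.2.5 tabulates patients without a late test, with reasons. Neither gives an SVR12 rate restricted to followed patients, so the concern survives in that narrower sense.
- *The shift will be several points, comparable with the planned interval width.* That needs an untested share of about 4% of enrolment, which nothing in the documents suggests. HCV RNA is scheduled at every on-treatment and post-treatment visit, even though testing is not mandated.

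**Conclusion.** The point holds as a defect of definition. On the literal text of SAP 4.2.1, a CP patient with only a baseline HCV RNA value enters CPSFU as a failure; under the list in protocol 9.7.1 the same patient is outside it. The CPSFU12 sensitivity analysis, the SVR24 rate and the interim non-response table are exposed. Primary SVR12 is not.

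The effect is about 0.2 percentage points per patient: 0.9 points with an assumed 4 such patients at 95% response. Set against planned interval widths of 5 to 6 points, a handful of patients is a small shift. The figures assume a baseline value of at least 50 IU/mL, about 418 other CPSFU patients, and a programmer who follows the SAP wording as it stands. It should be corrected because a sufficient-follow-up population should not contain patients with no follow-up measurement, and because the correction is cheap.

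**What to change.** - In SAP 4.2.1, limit the second and third CPSFU criteria to the last *post-baseline* HCV RNA measurement, for both CPSFU12 and CPSFU24.
- Rewrite the closing sentence in SAP 4.2.1 and protocol 9.7.1 so that patients with no post-baseline HCV RNA measurement are also excluded, and bring the protocol abstract into line.
- Decide explicitly about patients with no post-baseline test who stopped for safety reasons or have a reported virologic failure. With the restriction restored, criterion 3 does not admit them. If they are to be kept, add a separate fourth criterion; an exception placed only in the closing sentence would again set the summary against the list.
- SAP 4.2.9 describes the interim non-response table in the past tense, so state which rule was used there.

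The cost is a few lines of text in each document and one derivation condition. CPSFU becomes slightly smaller. SAP 4.2.5 already tabulates reasons for exclusion from each population, so the number of patients removed would be visible there.

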#### **Confidential Information**

due to reasons related to safety (e.g. dropped out due to adverse event) or incomplete efficacy information (e.g. virologic failure such as relapse is reported in the electronic case report form (eCRF) but date and value of the corresponding HCV RNA test is missing). The safety population (SP) is defined as all patients who received at least one dose of the ABBVIE REGIMEN.

Descriptive and exploratory statistical methods will be used to analyze the data of the study. All baseline and disease characteristics will be summarized for the CP stratified by the CP analysis groups (based on genotype 1 subtype, fibrosis status, treatment experienced or naïve), which are relevant for scheduled treatment combination ( $\pm$  dasabuvir,  $\pm$  RBV) and duration (12 or 24 weeks). In addition, baseline summaries will be repeated for the SP and TP without stratification into subgroups. Further details of analysis populations and the CP analysis groups will be specified in the statistical analysis plan (SAP).

The primary effectiveness analysis will be performed for CP patients, stratified by the CP analysis groups. Response rates (i.e. SVR12 rate, end of treatment [EoT] response rate, relapse rate, viral breakthrough) will be determined for the various CP analysis groups. The relapse rates will be estimated in patients of the CP analysis groups with EoT response and sufficient HCV RNA measurements post treatment. Viral breakthrough rates will be estimated in all patients of the CP analysis groups, who have at least one undetectable HCV RNA measurement on treatment and at least one on-treatment or EoT measurement thereafter. For all rates specified above 95%-confidence intervals (CIs) will be determined using the Clopper-Pearson method.

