4.2.8 Analyses of Safety

All safety variables will be summarized for patients in the SP using descriptive statistical methods stratified by treatment regimen and cirrhosis status and overall.

An overview of tables for the individual values is given in Table 12.

The layouts of the tables mentioned above are provided in Part II of the SAP (Table Shells).

4.2.8.1 *Exposure to Study Medication*

One table will show the frequencies for early discontinuation and exceedance of Abbvie Regimen or Ribavirin and the corresponding reasons for SP by treatment regimen and cirrhosis status. The Abbvie Regimen is considered to have been prematurely discontinued if actual duration is shortened for more than 7 days. The duration for taking Abbvie regimen is considered to have been exceeded if the actual duration is prolonged for more than 7 days. Furthermore, summary statistics will be generated for the duration of ABBVIE regimen taken and the duration of ribavirin taken, i.e. n, mean, median, standard deviation [SD], minimum, maximum.

Unintended medication errors, i.e. patient missed taking Paritaprevir/r-Ombitasvir or Dasabuvir for at least 7 days in a row, will be displayed by medication for the entire treatment period.

4.2.8.2 *Co-medication*

Treatments, surgical and medical procedures will be coded by AbbVie assigning appropriate preferred and class terms. Frequencies will be displayed for SP by treatment regimen and cirrhosis status.

In one table, the co-medication (preferred term) will be grouped by class. Only co-medication received during treatment specified by ABBVIE regimen will be displayed (Treatment profiles: A1, A2, C1 Drug B, C2 Drug B, C3 Drug B, D).

In another table the co-medication (preferred term) will be grouped by profile. All treatment profiles will be considered, i.e.:

- A1: Continued (A1)
- A2: Permanently discontinued during CHC treatment (A2)
- A3: Permanently discontinued prior to CHC treatment (A3)
- B: Discontinued prior to CHC treatment and reintroduced post-treatment (B)
- C1 Drug A: Permanently replaced at start of CHC treatment (C1A)
- C1 Drug B: Substitute at start of CHC treatment and discontinued during CHC treatment (C1B)
- C2 Drug A: Permanently replaced at start of CHC treatment (C2A)
- C2 Drug B: Substitute at start of CHC treatment and continued (C2B)
- C3 Drug A: Replaced during CHC treatment (C3A)
- C3 Drug B: Substitute during CHC treatment (C3B)
- D: Introduced during CHC treatment (D)

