Creatinine Clearance [mL/min]	>= 75	< 75 - 60	< 60 - 30	< 30 – 15	< 15

Table 12 Overview of Outputs for Safety Variables

Output Title	Output Short Name	Analysis Population
Exposure to Study Medication by Treatment Regimen and Cirrhosis Status - SP - <country>	tesm_<c>_tc_sp	Safety population
Unintended Medication Error /Pregnancy by Treatment Regimen and Cirrhosis Status -- SP - <country>	tum_<c>_tc_sp	Safety population
Treatment-emergent AEs by Treatment Regimen and Cirrhosis Status - SP - <country>	tae_<c>_tc_sp	Safety population
Serious Treatment-emergent AEs by Treatment Regimen and Cirrhosis Status - SP - <country>	tsae_<c>_tc_sp	Safety population
Non-Serious Treatment-emergent AEs by Treatment Regimen and Cirrhosis Status - SP - <country>	tnsae_<c>_tc_sp	Safety population
Treatment-emergent AEs by Severity by Treatment Regimen and Cirrhosis Status - SP - <country>	taes_<c>_tc_sp	Safety population
Treatment-emergent AEs Leading to Death by Treatment Regimen and Cirrhosis Status - SP - <country>	taed_<c>_tc_sp	Safety population
Treatment-emergent AEs Leading to Hospitalization by Treatment Regimen and Cirrhosis Status - SP - <country>	taeh_<c>_tc_sp	Safety population
Treatment-emergent AEs Possibly Related to ABBVIE Regimen by Treatment Regimen and Cirrhosis Status - SP - <country>	taera_<c>_tc_sp	Safety population
Treatment-emergent AEs Possibly Related to Ribavirin in Patients taking RBV by Treatment Regimen and Cirrhosis Status - SP - <country>	taerr_<c>_tc_sp_RB V	Safety population: patients taking RBV
Treatment-emergent AEs Caused by Medication Error - Paritaprevir/r-Ombitasvir - by Treatment Regimen and Cirrhosis Status - SP - <country>	taempo_<c>_tc_sp	Safety population
Treatment-emergent AEs Caused by Medication Error - Dasabuvir - in Patients taking 3DAA by Treatment Regimen and Cirrhosis Status - SP - <country>	taemd_<c>_tc_sp_3d aa	Safety population: patients taking 3DAA
Treatment-emergent AEs Leading to Withdrawal of ABBVIE Regimen by Treatment Regimen and Cirrhosis Status - SP - <country>	taewa_<c>_tc_sp	Safety population
Treatment-emergent AEs Leading to Withdrawal of Ribavirin in Patients taking RBV by Treatment Regimen and Cirrhosis Status - SP - <country>	taewr_<c>_tc_sp_RB V	Safety population: patients taking RBV
Listing of SAEs - SP - <country>	lsae_<c>_sp	Safety population
Glossary for AEs - <country>	tgae_<c>	-
Co-medication by Treatment Regimen and Cirrhosis Status - SP - <country>	tcom_<c>_tc_sp	Safety population

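### The SAP limits the safety population to dosed patients whose prescribed regimen is known, a condition the protocol does not set and the SAP does not declare as a change

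*SAP*

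**What the plan says.** Protocol 9.7.1 sets one condition: "The Safety Population (SP) is defined as all patients who received at least one dose of the ABBVIE REGIMEN". The Data Analysis part of the protocol abstract gives the same definition.

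The safety population paragraph of SAP 4.2.1 starts from all enrolled patients and keeps the dose condition, then adds a second sentence, so that it covers those who "received at least one dose of the ABBVIE REGIMEN. The prescribed ABBVIE REGIMEN needs to be known". The same second sentence stands in the SAP's target population, so the core, non-core and sufficient-follow-up populations inherit it.

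SAP 4.2.8 ties the safety analysis to this population: "All safety variables will be summarized for patients in the SP using descriptive statistical methods stratified by treatment regimen and cirrhosis status and overall". In SAP Table 12 this covers, among others, "Listing of SAEs - SP - <country>" and "Treatment-emergent AEs Leading to Death by Treatment Regimen and Cirrhosis Status - SP - <country>".

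**The concern.** A safety population is normally fixed by exposure alone, so that completeness of the record cannot decide whose events are counted. Here a patient known to have taken the drug can be left out because one item is blank. The narrowing is also silent. The SAP says openly that it departs from the protocol for the upper bound of the SVR12 window (4.1.1), the laboratory shift tables (4.2.8.4) and the interim analysis (4.2.9), but has no such note here.

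At stake is the completeness of the counts of serious events and deaths. These are likely to be small, and in a listing of individual SAEs a single missing patient matters.

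**Working it through.** The plan states no figure on this point, so there is none to reproduce. The check traces the populations and then gives a scaled illustration.

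**1. Who is affected.** The protocol's abbreviation list defines the regimen as paritaprevir/r and ombitasvir with or without dasabuvir; ribavirin is named separately. An unknown ribavirin prescription therefore does not appear to trigger the exclusion. The affected patient has a documented dose but no record of which regimen was prescribed.

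**2. Do other outputs recover the events?**
- SAP Table 12: every output with a named population uses the safety population or a subset of it. The two coding glossaries (adverse events, co-medication) name no population. The adverse event glossary is described as showing verbatim and coded terms, not counts.
- SAP 4.2.7.2.1: the death category among SVR12 non-responders is tabulated for the core population, which carries the same condition.
- SAP 4.2.5: death as a reason for not completing the study is tabulated for the safety and core populations only.
- SAP 4.2.5 and 4.2.10: for all enrolled patients, exclusions and their reasons are summarised and listed. No adverse event content is promised. The table shells are not in the documents, so the exact columns of that listing cannot be checked.

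No described table or listing gives these patients' adverse events.

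**3. Does the layout force the exclusion?** No. The safety population groups in SAP 4.2.1 have a Total column in each block, and patients with unknown fibrosis status have a block of their own. Elsewhere too the SAP keeps incomplete records: events without an onset date count as treatment-emergent (4.2.8.3), and co-medication without a profile has its own category (4.2.8.2).

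**4. Illustration.** Inputs: N = 440, the planned enrolment (protocol 9.5), all taken as dosed. The share f with unknown regimen and the SAE risks are assumptions; the documents give neither.
- Patients left out: m = 440 × f, rounded.
- With a 3% SAE risk in everyone, the chance that at least one patient with an SAE is missing is 1 − 0.97^m. The expected reported rate does not change.
- With a 20% risk among those left out and 3% in the rest, the rate in all dosed patients is [0.03 × (440 − m) + 0.20 × m] / 440, against 3.00% reported. The share of SAE patients lost is 0.20 × m / [0.03 × (440 − m) + 0.20 × m].

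| f | m | Chance of at least one missing (3% risk) | Rate in all dosed (20% risk if unknown) | Share of SAE patients lost (20% risk) |
|---|---|---|---|---|
| 0% | 0 | 0% | 3.00% | 0% |
| 0.5% | 2 | 6% | 3.08% | 3% |
| 1% | 4 | 12% | 3.15% | 6% |
| 2% | 9 | 24% | 3.35% | 12% |
| 5% | 22 | 49% | 3.85% | 26% |

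For m = 4: 1 − 0.97^4 = 0.115; (13.08 + 0.80) / 440 = 3.15%; 0.80 / 13.88 = 5.8%.

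**The case against.** A reader might infer that the rule selectively removes patients who stopped early, were hospitalised or died, because their records are the poorest. The documents do not support that. The condition concerns the prescribed regimen. Prescription comes before the invitation to take part (protocol 9.1), the regimen is an inclusion item (9.4.1.1), and its initiation is documented at baseline (Table 2). It would normally be on file before any on-treatment event. Electronic checks must be resolved before a module can be completed, and queries follow (9.6.1). Protocol 9.4.1 says data are recorded if available in the charts. That makes a gap possible, but does not tie it to outcome.

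A reader might also infer that the events vanish altogether. They do not. SAEs still go to the sponsor within 24 hours (protocol 11.5), the glossaries are not restricted to the safety population, and disposition shows who was excluded and why.

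It can further be said that the protocol leaves details of the analysis populations to the SAP, and that regimen, as the exposure by which tolerability is stratified, need not be handled like fibrosis status.

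These points limit the size of the problem, and the affected group may be empty. They do not remove it. Leaving details to the SAP does not readily cover a new exclusion from a population the protocol has already defined, and the Total columns can hold a patient of unknown regimen.

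**Conclusion.** The point stands as an undeclared narrowing of the safety population that can leave exposed patients out of all planned adverse event tables and the SAE listing. It rests on the text alone: one condition in the protocol, two in the SAP, and no described output that restores the missing events.

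The size is unknown. If every dosed patient has a recorded regimen, the effect is zero. Under the assumed 0.5% to 5% unknown and a 3% SAE risk, the chance of at least one missing SAE patient is about 6% to 49%, with no expected bias in the rate. The bias columns in the table apply only if the excluded patients carry a higher risk, which the documents do not show. The change should be made because it restores the protocol's definition at little cost, not because a material loss has been demonstrated.

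**What to change.** In the safety population definition of SAP 4.2.1, delete "The prescribed ABBVIE REGIMEN needs to be known", so that at least one dose is again the only exposure condition. Keep the sentence in the target population.

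Count dosed patients with an unrecorded regimen in the Total columns of the safety population tables, and show them in the SAE listing marked as regimen unknown. Separate regimen-unknown columns are not needed.

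The cost is one deleted sentence and a footnote to the safety population tables, since the regimen columns may no longer sum to Total. If no such patient exists, no result changes. If the sponsor prefers to keep the condition, the SAP should declare it as a departure, justify it, and list the adverse events of any dosed patient it excludes.
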